## What is already known about this subject?

### What does this study add?

Total knee arthroplasty (TKA) is considered the gold standard management for advanced knee osteoarthritis, however around 20% of the patients still complain of persistent knee pain after the operation. This study will add a new concept of combining genicular nerve radio-frequency ablation (GNRFA) with TKA In a hypothesis to improve functional outcome, post-operative pain and quality of life.

## 1. Introduction/Review

Total knee arthroplasty is a very common operation, and its incidence is believed to increase furthermore in the near future. That's why there are a lot of studies focused on improving the patient's satisfaction rate, while the unsatisfied patients remain to vary from 10%-30% without any noticeable complications. Early post operative rehabilitation and fast track protocols showed improvement in functional outcome and pain relief but are still hindered by the patients compliance. The idea of implementing genicular nerve radio-frequency ablation in combination with TKA rose when GNRFA showed significant improvement in patients with chronic knee osteoarthritis, studies showed pain relief up to 67% at the first 3 months, yet alone it has a very slim indications as it addresses only the biological aspect of the knee osteoarthritis without resolving the mechanical problem that will continue to progress over time. Other studies showed positive outcome of GNRFA in cases of chronic knee pain after TKA.

Given that data, combining GNRFA with TKA might give the patient a better chance to proceed with early rehabilitation programs improving the functional outcome, while decreasing postoperative pain is also considered an important factor of patients' satisfaction and quality of life enhancement.

## 2.Aim/Objectives

To compare between conventional Total Knee Arthroplasty (TKA) and Total Knee Arthroplasty (TKA) combined with intra-operative Genicular Nerve Radio-Frequency Ablation (GNRFA), concerning post-operative functional outcome and pain scores in patients with advanced knee osteoarthritis.

## 3.Methodology

- **Type of the study:** Randomized controlled clinical trial
- **Study setting:** Ain Shams University hospitals
- **Study period:** 24 months
- **Study population:** Patients with advanced knee osteoarthritis

### Inclusion criteria:

- Both sexes
- Age from 50-80 years old

### Exclusion criteria:

- Patients unfit for surgery
- Patients underwent previous GNRFA

- **Sampling method:** Convenient sample
- **Sample size:** 70 knees will be randomly divided by a computer-generated sequence in to 2 groups:
  - Group A ( $\approx$ 35 knees): will undergo TKA
  - Group B ( $\approx$ 35 knees): will undergo TKA combined with GNRFA
- **Ethical considerations:** will be followed by obtaining the hospital research/ethics committee approval and written informed consents from the patients.

- **Study tools:**

- **Preoperative diagnosis and evaluation:**

- **Clinical Evaluation:**

- History
      - General examination
      - Local examination (pre-operative)

- **Radiological Evaluation:**

- Plain X-ray antero-posterior standing view of the diseased knee.
      - Plain X-ray lateral view of the diseased knee.

- **Laboratory investigations:**

- Routine preoperative lab investigations

- **Operative technique:**

Patients will be operated using standard mid-vastus approach, conventional GNRFA

- **Post-operative management:**

- Proper antibiotic and standardized analgesics protocol will be given post-operative
      - Prophylaxis against DVT
      - Post-operative x-rays will be done, Plain X-ray antero-posterior and lateral view of the operated knee.

- **Follow up strategy:**

Patients will be reviewed after 2 weeks to check their wounds and for sutures removal, then the follow up will be every month in the first 6 months then every 3 months till the end of the study (2 years). The follow up will include:

➤ **Clinical and functional assessment:**

- Oxford knee score to assess the function.
- Visual analogue scale (VAS) to assess pain.
- Emotional acceptance/ Patient satisfaction.

➤ **Radiological assessment:**

Plain X-ray as described before at every follow up visit.

- **Statistical Analysis:** Statistical package for social science (SPSS 15.0.1 for windows; SPSS Inc., Chicago, IL, 2001). Data will be presented as Mean and Standard deviation (+/-SD) for quantitative parametric data, and Median and Interquartile range for quantitative non-parametric data. Frequency and percentage will be used for presenting qualitative data. Suitable analysis will be done according to the type of data obtained. P<0.05 will be considered significant.
- **Statistical package:** data entry and statistical analysis of the collected data will be performed using a reliable software program.

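### Does a follow-up that ends at the close of a 24-month study leave the length of follow-up per knee undefined?

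*Protocol*

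**What the plan says.** Under Methodology, the Protocol states "Study period: 24 months". The Follow up strategy item in the same section sets a wound check at 2 weeks; "then the follow up will be every month in the first 6 months", and "then every 3 months till the end of the study (2 years"). The Oxford knee score, the pain VAS, satisfaction and plain X-rays belong to these follow-up visits.

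On entry to the study, the Protocol says "70 knees will be randomly divided by a computer-generated sequence in to 2 groups", with about 35 knees in each, and "Sampling method: Convenient sample". It gives no recruitment window, month of last surgery or minimum follow-up per knee.

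The opening section motivates the trial by noting that "around 20% of the patients still complain of persistent knee pain after the operation". The Introduction also points to relief in the first 3 months after ablation and to easier early rehabilitation. The Aim names function and pain after the operation, without a time point.

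**The concern.** The visit schedule starts on one clock and stops on another. The early visits count from each operation, while the last visit is tied to the end of the study. Seventy knees cannot all be operated on the first day, so the two clocks must drift apart by the time that recruitment takes.

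A reader who takes the two years as a promise to each knee finds that the study must last longer than 24 months. A reader who takes it as a calendar close finds that follow-up varies between knees, with a minimum that is not written down. Study duration and follow-up per participant are normally stated in a protocol, so this cannot simply be assigned to a separate analysis plan.

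At stake would be the later visits. Persistent pain after surgery is the stated motivation, and the knees operated last are the ones with the fewest late assessments. If the protocol promised two years for every knee and the timetable could not deliver them, late results would rest on fewer knees than a reader expects.

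**Working it through.** **Inputs from the Protocol.** Study period 24 months; follow-up to the end of the study, given as 2 years; visits at 2 weeks, monthly to month 6, then 3-monthly; 70 knees. **Assumed, because the Protocol does not give it:** recruitment time R, taken as 3, 6, 12 and 18 months, with uniform entry and no dropout.

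**Step 1. Compare the two stated figures.** 24 months / 12 = 2 years. One is labelled as the study period and the other as the end of the study. They are equal and describe the same event.

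**Step 2. Calendar close at month 24 (the plain reading).** A knee operated in study month s is followed for 24 - s months. The minimum is 24 - R and the mean is 24 - R/2. A schedule reaching month 24 has 13 visit times: 0.5; 1 to 6; 9, 12, 15, 18, 21, 24. The last-operated knee has those at or before 24 - R.

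| R (assumed) | Minimum follow-up, 24 - R | Mean follow-up, 24 - R/2 | Visits, last knee |
|---|---|---|---|
| 3 | 21 | 22.5 | 12 |
| 6 | 18 | 21 | 11 |
| 12 | 12 | 18 | 9 |
| 18 | 6 | 15 | 7 |

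Every knee reaches month 6 when 24 - R >= 6, that is R <= 18. Every knee reaches month 12 when R <= 12. At R = 18 the number reaching month 12 is 70 x (24 - 12)/18 = 46.7, about 47 knees.

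**Step 3. Two years for each knee (the alternative reading).** Total duration would be 24 + R, or 27, 30, 36 or 42 months for the four values of R. This equals the stated 24 only if R = 0. To avoid the conflict, the study period would have to mean follow-up per knee, and the end of the study would have to mean the end of each knee's own follow-up. Both labels refer to the study, so this reading strains the text twice.

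**Step 4. Effect on the comparison.** The closing date is the same for both groups, and group is assigned by a computer-generated sequence. The month of surgery, and hence the available follow-up, is therefore unrelated to group apart from chance. At any visit, the knees compared are at the same time since surgery. Truncation is fixed by the calendar and not by how the patient fares. Fewer knees at late visits reduce precision there, but do not shift the contrast between groups.

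**The case for a change.** The strongest case for a change is that even the plain reading leaves each knee's follow-up unquantified. The motivating problem is pain that persists, so late visits carry part of the question. Under the longer recruitment times the shortfall falls entirely on those visits: after month 12 for R = 12 and after month 6 for R = 18. The number of X-rays per knee also depends on the reading, 13 on a schedule reaching month 24 against 7 for the last knee at R = 18. One sentence would settle the matter.

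It stands that the recruitment window is absent, and that a reader cannot work out the minimum follow-up without it. It also stands that a clarifying sentence would be cheap. The rest does not carry.

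- A shortfall needs a promise to fall short of. Two years for all 70 knees is not what the text says, so setting expected visits against a full 24-month schedule for everyone measures loss from a plan that was not made.
- The opening section attaches no duration to persistent pain. The Introduction's argument concerns the first 3 months and early rehabilitation, and the Aim fixes no late time point. Visits to month 6 are complete for every knee for R up to 18, apart from dropout.
- Every value of R above is an assumption. The calculation shows what would follow from each, not that the document is wrong.

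**Conclusion.** No change to the plan is needed. The Methodology section is consistent on its plain reading: the study closes at 24 months, visits are timed from surgery until that close, and knees operated later are followed for less time. This is an ordinary design and a fair trade-off for a single-institution trial of 70 knees.

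The remaining gap is the recruitment window, and so the minimum follow-up of 24 - R months. For R from 3 to 18 months that minimum runs from 21 down to 6 months. The sponsor knows R, and an analyst would as a matter of course report the recruitment dates and the number of knees seen at each visit by group. Stating the month of last surgery, and whether the two years run from study start or from surgery, would be a helpful clarification. It would leave the sample size, visits, assessments and comparison as they are.

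The conclusion rests on the calendar-close reading, on a common closing date for both groups, and on recruitment of no more than 18 months for complete data to month 6. If the sponsor had in fact intended both a 24-month total and two years for each knee, the two would conflict for any R above zero, but the text does not say so.

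### No pre-operative Oxford knee score or VAS is scheduled, so the follow-up comparison has no outcome baseline for adjustment or for describing the groups at the start

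*Protocol*

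**What the plan says.** The aim (Protocol, section 2) is to compare the two groups "concerning post-operative functional outcome and pain scores in patients with advanced knee osteoarthritis".

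In section 3, the pre-operative evaluation has three parts:

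- **Clinical:** history, a general examination and "Local examination (pre-operative").
- **Radiological:** two plain X-ray views.
- **Laboratory:** "Routine preoperative lab investigations".

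None of these is itemised further, and none names an outcome score.

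The follow-up strategy starts with a wound check at 2 weeks. Visits are then monthly to 6 months, and "then every 3 months till the end of the study (2 years). The follow up will include" the outcome measures. Only here do the instruments appear: "Oxford knee score to assess the function" and "Visual analogue scale (VAS) to assess pain", together with patient satisfaction.

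On size and allocation, "70 knees will be randomly divided by a computer-generated sequence in to 2 groups" of about 35 each. Eligibility covers advanced osteoarthritis, "Age from 50-80 years old", fitness for surgery and no earlier nerve ablation. It sets no threshold for pain or function.

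**The concern.** Pain and function before surgery are natural candidates to predict pain and function afterwards. If the same scales are recorded before allocation, the analysis can remove that part of the between-patient variation, and the report can show how severe the condition was at entry and whether the groups began alike. As scheduled, the protocol provides for neither.

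The choice of model can be left to a statistical analysis plan, which is not at hand here. Whether a score is collected cannot: once a knee has been operated on, its pre-operative score is gone. Eligibility does not fill the gap, because without a pain or function threshold it does not fix the starting level.

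The stake is limited. Randomisation protects the comparison of post-operative scores from bias, and the aim promises no change from baseline. The loss is in precision and description, not validity.

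**Working it through.** **Reading check.** Setting the two lists in section 3 side by side:

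| Item | Pre-operative evaluation | Follow-up |
|---|---|---|
| History, general and local examination | listed | – |
| Plain X-rays | listed | listed |
| Routine laboratory tests | listed | – |
| OKS | not listed | listed |
| VAS | not listed | listed |

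No other section schedules either score before surgery.

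**Plan's own figure.** The 70 knees cannot be reproduced, because the protocol gives no effect size, SD, power or dropout. What follows takes 70 as given and illustrates what a baseline score could add.

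**Inputs.**
- From the protocol: 35 knees per group, significance at 0.05.
- Assumed: two-sided testing; outcome SD set to 1; independent knees; complete data at one follow-up time; baseline to follow-up correlation r from 0.1 to 0.6.

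**Unadjusted comparison.**
- SE of the difference = √(2/35) = 0.239 SD.
- 95% half-width = t(68) × SE = 1.995 × 0.239 = 0.477 SD.

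**Adjusted for baseline (ANCOVA).**
- Residual variance is multiplied by 1 − r².
- Half-width = t(67) × 0.239 × √(1 − r²), with t(67) = 1.996.
- Equivalent number of unadjusted knees = 70/(1 − r²).
- Estimating the slope costs, on average, a further factor of 1 + 1/66 = 67/66. The net variance factor is then (1 − r²) × 67/66, and the net equivalent is 70 divided by that factor.

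| r | 1 − r² | Half-width (SD) | Equivalent knees | Net factor | Net equivalent knees |
|---|---|---|---|---|---|
| 0.1 | 0.99 | 0.475 | 71 | 1.005 | 69.7 |
| 0.2 | 0.96 | 0.467 | 73 | 0.975 | 71.8 |
| 0.3 | 0.91 | 0.455 | 77 | 0.924 | 75.8 |
| 0.5 | 0.75 | 0.413 | 93 | 0.761 | 91.9 |
| 0.6 | 0.64 | 0.382 | 109 | 0.650 | 107.7 |

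**Break-even.** (1 − r²) × 67/66 = 1 gives r = √(1 − 66/67) = 0.122. Below this, adjustment gains nothing.

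**Worst case.** At r = 0 the factor is 67/66 = 1.015, a cost of about 1.5% in variance. 70/1.015 = 69.0, so this is 1 knee.

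**Simulation check.** With 40,000 trials per correlation and the slope estimated in each, the ratio of adjusted to unadjusted variance was within 0.01 of the net factor at every r, including r = 0.

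**Same result as detectable difference.** With 80% power (normal approximation), (1.960 + 0.842) × 0.239 = 0.67 SD unadjusted. Multiplying by √(1 − r²) gives 0.66, 0.64, 0.58 and 0.54 SD at r = 0.2, 0.3, 0.5 and 0.6.

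**Description.** The difference between groups in mean baseline score also has an SE of 0.239 SD. A chance imbalance above 0.25 SD in either direction therefore has probability of about 30% (0.25/0.239 = 1.05 standard errors). The unadjusted confidence interval already allows for this, so it is not a further loss of precision. But without the scores nobody could see it.

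**The case against.** The strongest case against has four parts.

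1. **It argues from silence.** The pre-operative entries are bare labels, and a surgeon may well take an OKS or VAS under history or local examination. That is possible, but the protocol does not require it. It names both instruments at follow-up and neither before surgery, and unstandardised notes would not be on the outcome scale. The supportable statement is that the scores are not provided for. It is not that they certainly will be absent.

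2. **The stated aim is not defeated.** This stands. The post-operative comparison is valid without a baseline, and the protocol contradicts nothing. Age, sex, history, X-rays and laboratory results will still describe the groups. Only the outcomes' own starting values are missing.

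3. **The size is assumed throughout, and the range includes no gain.** This also stands. The correlation may differ between OKS and VAS and between visits. Allocation is by knee, and nothing excludes two knees from one patient, so treating knees as independent is a simplification. The figures illustrate the possible loss and do not measure it. The descriptive loss, however, remains even at a correlation of zero.

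4. **ANCOVA belongs in the analysis plan.** This is true of the model. It is not true of data collection, which is the part that cannot be repaired later.

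**Conclusion.** The concern holds. As written, the protocol schedules no pre-operative OKS or VAS, so it does not provide for adjusting the comparison for the outcome's own baseline or for describing starting pain and function on the outcome scales.

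Confidence is high on the reading and low on the size of the gain. Under the assumptions above, the precision forgone runs from nothing (correlation up to about 0.12) to moderate (about 36% of residual variance at 0.6, before the small cost of the slope). The balance favours collecting the scores: the worst case costs about 1 knee, while a correlation of 0.5 would add the equivalent of about 22 knees (91.9 − 70). The trial's validity is not in question. This is something the sponsor should correct, not a fatal flaw.

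**What to change.** Add OKS and VAS to the pre-operative evaluation in section 3, recorded before randomisation so that knowledge of the group cannot influence the answers. Report both by group. State that each baseline score will be a covariate (ANCOVA) when the matching follow-up score is compared; model details can go in the statistical analysis plan.

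The cost is one short questionnaire and one pain scale at a contact that already takes place, plus one covariate per model. The downside is a few minutes of patient time and, if baseline proves uncorrelated with follow-up, about 1.5% in variance. Groups, visits and sample size are unchanged. The change helps only knees not yet operated on, so it should be made early.

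### The protocol names no primary outcome and no primary time point or summary over visits, so its only decision rule, P<0.05, is attached to no comparison

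*Protocol*

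**What the plan says.** The aim (Protocol, 2.Aim/Objectives) is to compare the two operations "concerning post-operative functional outcome and pain scores in patients with advanced knee osteoarthritis". Function and pain stand side by side, with no ranking and no time point.

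The follow-up strategy (Protocol, 3.Methodology) has a 2-week wound review, then visits "every month in the first 6 months then every 3 months till the end of the study (2 years"). The assessments are the Oxford knee score for function, VAS for pain, and emotional acceptance or patient satisfaction. None is called primary or main, and no visit, change score or average is singled out.

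The sample size entry says "70 knees will be randomly divided by a computer-generated sequence" into two groups of about 35. It gives no outcome, effect size, standard deviation or power.

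The inferential text is two sentences: "Suitable analysis will be done according to the type of data obtained" and "P<0.05 will be considered significant".

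**The concern.** A significance threshold controls error only for a comparison fixed in advance. Here the threshold is fixed and the comparison is not. The sample size does not identify a main outcome indirectly either, because no outcome stands behind the 70 knees.

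Two consequences follow:

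- **No pre-stated reading of a mixed result.** Function and pain can disagree, and so can early and late visits. If VAS were better at month 2 and the Oxford knee score no different at any visit, the protocol could not say whether the aim was met. Either answer could be chosen after the data are seen.
- **No demonstrated 5% error rate.** Any of the outcome-by-visit comparisons relevant to the aim could be put forward as the result at P<0.05.

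The study period adds a practical difficulty. It is 24 months, the same length as the follow-up. If it includes recruitment, later patients cannot reach the last visits, so the time point has to be chosen deliberately.

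**Working it through.** **The plan's own figure.** The 70 knees cannot be reproduced, because the protocol gives no effect size, standard deviation, power or drop-out rate.

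**Visits.** Monthly to month 6 gives 6 (months 1-6). Every 3 months to month 24 gives 6 more (months 9, 12, 15, 18, 21, 24). The total is 12. The 2-week review is described as a wound and suture check and is not counted. Six visits is used as a second case, for patients with short follow-up.

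**Comparisons relevant to the aim.** 2 outcomes × 12 visits = 24; 2 × 6 = 12.

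**Upper reference.** If all tests were independent, the chance of at least one P<0.05 with no true effect would be:

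- 24 tests: 1 − 0.95^24 = 0.708
- 12 tests: 1 − 0.95^12 = 0.460

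Repeated scores on the same knees are correlated, so these values will not be reached.

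**With correlation.** The assumptions, none of them from the protocol, are: no true effect, independent knees, and unadjusted two-sided tests of both outcomes at every visit. Visit correlation is 0.5, 0.7, 0.8 or 0.9, and outcome correlation is 0.4, 0.6 or 0.8. The correlation between different outcomes at different visits is the product of the two. For each setting, 200,000 draws of jointly normal z-statistics give P(max|z| > 1.96):

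| Visit pattern | 12 visits (24 tests) | 6 visits (12 tests) |
|---|---|---|
| Equal correlation 0.5-0.9 between all visits | 0.20-0.52 | 0.16-0.36 |
| 0.5-0.9 between adjacent visits, decaying by visit order | 0.31-0.63 | 0.20-0.40 |

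The two rows rest on different assumptions. In the second, with an adjacent correlation of 0.5, the first and last of 12 visits correlate at 0.5^11 = 0.0005, far below 0.5. That row also ignores the wider spacing after month 6.

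**One named comparison.** Under the same assumptions, one outcome at one visit gives 0.050, and one outcome summarised by its standardised mean over 12 visits gives 0.049-0.051.

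**What 35 per group can detect at 80% power, in SD units.** The normal approximation is d = (z for alpha + 0.842) × √(2/35), with √(2/35) = 0.239.

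- One primary comparison, two-sided 0.05: (1.960 + 0.842) × 0.239 = 0.67. A two-sample t test gives 0.68.
- Two primary outcomes at 0.025 each: (2.241 + 0.842) × 0.239 = 0.74. A two-sample t test gives 0.75.

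These ignore drop-out and two knees from one patient.

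**The case against.** The strongest reply is that a statistical analysis plan may exist, and that one longitudinal model per outcome would fit the protocol's words as well as visit-by-visit testing. That stands as far as methods go: modelling of visits, adjustment, and test order for secondary outcomes may sit in the SAP and are not criticised here. It does not cover the main outcome and its time frame. These define the trial's question and the basis of its sample size, so they belong in the protocol.

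A reader might infer three stronger points, none of which the protocol supports:

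- **That every outcome will be tested at every visit.** The protocol neither says so nor rules it out. The percentages illustrate what the wording permits; they do not describe the plan.
- **That satisfaction should be counted too.** Three outcomes at 12 visits make 36 tests, with a chance of about 24-65% under equal visit correlation and up to 76% under decay. But the aim names only function and pain. Satisfaction appears only in the follow-up list, so the two-outcome figures are the relevant ones.
- **That the missing quality-of-life measure is a further error.** The opening rationale hopes "to improve functional outcome, post-operative pain and quality of life", but the aim omits quality of life and the introduction treats it as a benefit expected from less pain. It is background, not a planned comparison.

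**Conclusion.** The concern holds as an omission in the protocol. No outcome is primary, no time point or summary over visits is chosen, and P<0.05 decides nothing in particular. This rests on the text alone and needs no assumption.

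The size of the consequence does depend on assumptions. With the aim's two outcomes tested unadjusted at every visit and independent knees, the chance of at least one false positive is about 20-52% over 12 visits and 16-36% over 6, with equal between-visit correlation of 0.5-0.9. It is about 31-63% and 20-40% if that correlation applies only to adjacent visits and decays. In every setting examined it is well above 5%. The point should be fixed, but its weight comes from the missing primary comparison and not from any one of these percentages.

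**What to change.** Before any outcome data are examined, amend the protocol in one of two ways:

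1. Name one primary outcome (for example the Oxford knee score or VAS) at one time point, or as one pre-stated summary over visits, tested two-sided at 0.05.
2. Since the aim pairs function and pain, name both as co-primary, each with its own time point or summary and a pre-stated split of alpha (for example 0.025 each).

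In either case, choose a visit or period that every patient will reach within the 24-month study period. Label all other outcomes and visits secondary, and state that none of them is proof of benefit on its own. Their modelling and test order may sit in the SAP. The choice of outcome is the investigators'.

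**Cost.** The change is to wording, with two consequences. Isolated significant results at other visits can no longer be claimed as the trial's result. The 70 knees also become checkable: with 35 per group, 80% power is reached only for the differences shown in the working, and the split of alpha raises that threshold. If a smaller difference matters for the chosen outcome, the sample size would have to be revisited.
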